1.0 Study Summary*

This is a pilot study of randomized clinical trial of Parent Acceptance and Commitment Therapy vs. an attention-control condition (placebo) for improving the mental health of parents of children with pediatric feeding disorder. The primary aims of this study are to evaluate feasibility and proof-of-concept.

2.0 Objectives*

2.1 Purpose, specific aims or objectives: Primary Aim: Test the hypothesis that PACT will result in clinically meaningful reductions in Mental Health(MH) problems among parents of children with Pediatric Feed Disorder (PFD) and identify factors that impact the feasibility of intervention delivery. This pilot study will involve conducting recruitment procedures for 4 months (or until parent N=30). Participants will be parents of 2- to 6-year-old children with PFD in outpatient treatment for their PFD. Parents will be randomly assigned to PACT or an attention control condition (control). Secondary aim: Test the hypothesis that PACT-F will result in clinically meaningful improvements in parent use of positive behaviors at meals, as measured through an observation of a representative mealtime.

2.2 Hypothesis: We will test the hypothesis that PACT results in clinically meaningful change in parent stress and anxiety, and parent use of positive mealtime behaviors, using the Reliable Change Index (RCI; success defined as $RCI > 1.96$). We anticipate that these procedures will be feasible, with feasibility success defined as recruitment rate above 60%, and retention, assessment completion, and intervention completion rate above 80%. Mixed methods data collection will identify factors that impact 1) recruitment rate (qualitative surveys, % meeting inclusion criteria, # of contact attempts), 2) retention rates (qualitative surveys, baseline characteristics; treatment group), 3) assessment completion rate (qualitative surveys, measure type), and 4) treatment completion rate (qualitative surveys, scheduling, treatment location).

3.0 Background*

Pediatric Feeding Disorder (PFD) is Prevalent, and Parents are Critical to Treatment Success. One-third of young children, and up to 80% of children with developmental delays, experience pediatric feeding disorder (PFD).¹ PFD is characterized by severely restricted volume or variety of foods and place children at increased risk for malnutrition.^{2,3} PFD is also associated with high financial burden.⁶ Interdisciplinary care to address medical and behavioral components of PFD is essential,^{33,34} and often involves a physician, psychologist, dietitian, and speech or occupational therapists.¹⁸ However, treatment success relies on the implementation of treatment recommendations at home by parents, including structured family meals, positive parent-child interactions at mealtimes, and use of behavioral strategies to reinforce feeding behaviors.³⁵

PFD is a Stressor to Parents. Many parents report distress when their child does not eat well as feeding is essential to survival.¹⁹ Each meal, then (occurring 3-5 times a day), is a

SHORT TITLE: PACT Study

potential stressor for parents of children with PFD. Many parents report “battles” with their children at mealtimes over eating.¹⁹ Parents across the spectrum of child age report similar experiences of mealtime distress.^{12,19,46}

Parents of Children with PFD are at Higher Risk for Mental Health (MH) Problems. Parents of children with PFD are at much higher risk for mental health (MH) problems (depression, anxiety, parenting stress, posttraumatic stress) than their peers,⁷⁻¹⁴ with up to 40% of parents endorsing MH problems.¹² In qualitative interviews, parents report an enduring emotional impact,¹⁹ including that difficulties feeding their young children negatively impacts their identity development as parents.¹⁹ This emotional impact has also been observed biologically, as one study found increases in parent cortisol when feeding their child with PFD.⁴⁷

Parent MH Problems Impact Health and Feeding Among Children with PFD. Parent MH problems are closely linked to poorer health outcomes in children with medical conditions such as poorer child quality of life, adherence to medical treatments, and mental health.⁴⁸⁻⁵⁶ Parent MH problems have been explicitly linked to problematic child feeding practices.¹⁵⁻¹⁷ Further, according to the child positive health model,⁵⁷ an innovative model for understanding child health, ecological systems⁵⁸ such as family factors shape child health. Thus, parent MH problems are critical to consider in relation to child health.

Parent-Focused MH Interventions May Improve Child Outcomes, but Uptake in Clinical Settings is Poor. Both pediatric feeding experts and parents have highlighted the need for interventions that specifically address parent MH problems in this population.^{18,19} Multiple recent studies have achieved promising results when testing the efficacy of psychological interventions (using Cognitive Behavioral Therapy & Problem Solving) for parent MH in other medical populations such as cancer.²⁰ However, these interventions are typically time and resource intensive (e.g., 6-12 sessions). Even among oncology care, where national standards²⁵ have declared that parent MH should be addressed with all families, uptake of evidence-based parent MH treatments are low.²⁵ Therefore, brief interventions that require minimal resources are essential.

Acceptance and Commitment Therapy (ACT) has the Potential to Radically Improve the Uptake of Parent MH Interventions and is Therefore Ideal for Parents of Children with PFD. ACT is a transdiagnostic treatment approach that is effective in treating a wide range of adult MH problems. Emerging studies have found it can be effective in as few as one session.²⁷ ACT focuses on changing how a person perceives and responds to negative thoughts and feelings, rather than focusing on challenging and eliminating these thoughts and feelings which can be more time intensive. ACT recently was adapted for parents of children with neurodevelopmental disorders (PACT), and a series of pilot studies found that PACT meaningfully reduced parent depression and anxiety, and improved child behavioral outcomes, in just 2-sessions.^{21,26,27} However, PACT has never been tested in a PFD population (nor has it been tested for problems other than anxiety and depression). If effective with parents of children with PFD, this brief treatment could radically increase the potential for uptake of parent MH treatment in PFD treatment clinics nationally.

Treatment Adaptations and Feasibility Testing are Critical Next Steps. In order to optimize the treatment for parents of children with PFD, our team has adapted PACT to meet the needs of parents of children with PFD using formative research methods (IRB# 00002321). Feasibility testing and proof-of-concept testing are the essential next steps before proceeding to an efficacy study.

4.0 Study Endpoints

Parents will complete the standard study battery at baseline, post-intervention, and 3-month follow-up.

Quantitative Measures. Feasibility success is defined as recruitment rate above 60%, and retention, assessment completion, and intervention completion rate above 80%.

SHORT TITLE: PACT Study

Demographics. Parents will provide information on their own and child's age, sex/gender, race/ethnicity, education, and socioeconomic status.

- Parent Mental Health (MH) Measures.
 - PHQ-9. A 9-item self-report measure of depressive symptoms. Scores of 10 or more indicate probable depression.
 - GAD-7. A 7-item self-report measure of anxious symptoms. Scores of 10 or more indicate probable anxiety.⁸⁷
 - IES-R. A 22-item self-report measure of posttraumatic stress symptoms. Scores of 33 or more indicate clinically significant posttraumatic stress.
 - PSS. A 10-item self-report measure of perceived stress. Scores of 14 or more indicate clinically significant stress.
 - AAQ-2. A 7-item self-report measure of psychological flexibility and experiential avoidance, which are targets of the behavioral treatment.
- Child Health.
 - PedsQL 4.0 (Generic). A 23-item parent-proxy measure of child quality of life, with versions specific to child age (2-4 years, 5-7 years) that each result in standardized total scores and domain-specific scores of physical functioning, emotional functioning, social functioning, and school functioning.
 - BPFAS. A 35-item parent-proxy report of child mealtime and feeding behavior.
- Qualitative Measures. Qualitative surveys will be completed by parents at the 3-month follow-up, focused on factors that impact feasibility. Feasibility of 1) recruitment procedures, 2) intervention procedures, and 3) measure completion.
- Observational Behavioral Coding. Parents will record a representative family mealtime over Microsoft Teams at baseline, post-intervention, and at 3-month follow-up. A research assistant will facilitate the recordings over Microsoft Teams using procedures routinely employed in [name] prior RCTs. The recordings will be coded using the Dyadic Interaction Nomenclature for Eating (DINE) coding scheme. The DINE is a well-established measure of mealtime behavior that has been studied in a variety of populations and has good psychometric properties.⁷⁴ The DINE measures parent-child interactions by coding three subscales: parent behaviors, child behaviors, and child eating behaviors. DINE coding will be completed by research assistants trained by the PI. The research assistants will be blinded to the intervention condition. Each video will be double-coded, and discrepancies will be resolved by meetings between the two coders and consultation with the PI.

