10.0 Procedures

[figure not shown]
Parents who meet inclusion criteria and sign consent will be randomized to either PACT-F or an attention control (control) condition using block randomization, such that an equal number of patients presenting for a new diagnosis and with an established diagnosis are randomized to each group. Participants will be blind to treatment condition (single blind study). See Figure 1 below for procedures. Intervention. Parents randomized to PACT-F will complete two 90-minute PACT-F sessions individually with a study interventionist, 2-weeks apart (see Table 2 for intervention content). Parents randomized to the control group will complete two 90-minute sessions individually with a study interventionist, 2-weeks apart (focused on nutrition education). The control intervention will be parallel to the PACT-F intervention in all ways, including interactive components and the face-to-face time with health professionals (interventionists). The control condition intervention has already been developed by [name] research team and covers a range of nutrition and healthy lifestyle topics including USDA's *MyPlate*. Interventionists for both conditions will be individuals with at least master's degree training in mental health or a related field. The interventions will take place remotely via telehealth. The team has expertise in remote delivery of therapy in both clinical and research environments. Both arms of the intervention will be manualized and interventionists in both arms will be trained using didactics and role playing with the PI. Intervention fidelity will be monitored by audio recording all sessions. The PI ([name]) will review video recordings each week and conduct weekly supervision.

Due to the nature of the study, the participants will be blinded to the group assignment during treatment. This is necessary as knowledge of whether they are in the treatment or control group may change behaviors of the participants. We will therefore not be able to give specific descriptions of the treatments in each group in the Informed consent form. Participants will be informed of their group assignment after they have completed the 3-month follow up and if they were in the control group be given the opportunity to participate in the treatment group. There is no difference in risk for either group.

Once the 3-month follow up is complete the subjects will be contacted and unblinded and control subjects will be offered the active treatment.

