
SHORT TITLE:

Figure 1

5.2 Blood and Other Specimen Collection:

N/A

11.0 Surveys and Psychometric Testing:

- Parent Mental Health (MH) Measures.
 - PHQ-9. A 9-item self-report measure of depressive symptoms. Scores of 10 or more indicate probable depression.
 - GAD-7. A 7-item self-report measure of anxious symptoms. Scores of 10 or more indicate probable anxiety.⁸⁷

SHORT TITLE:

- IES-R. A 22-item self-report measure of posttraumatic stress symptoms. Scores of 33 or more indicate clinically significant posttraumatic stress.
- PSS. A 10-item self-report measure of perceived stress. Scores of 14 or more indicate clinically significant stress.
- AAQ-2. A 7-item self-report measure of psychological flexibility and experiential avoidance, which are targets of the behavioral treatment.
- Child Health.
 - PedsQL 4.0 (Generic). A 23-item parent-proxy measure of child quality of life, with versions specific to child age (2-4 years, 5-7 years) that each result in standardized total scores and domain-specific scores of physical functioning, emotional functioning, social functioning, and school functioning.
 - BPFAS. A 35-item parent-proxy report of child mealtime and feeding behavior.
- Observational Behavioral Coding. Parents will record a representative family mealtime over Teams at baseline, post-intervention, and at 3-month follow-up. A research assistant will facilitate the recordings over Teams using procedures routinely employed in [name] prior RCTs. The recordings will be coded using the Dyadic Interaction Nomenclature for Eating (DINE) coding scheme. The DINE is a well-established measure of mealtime behavior that has been studied in a variety of populations and has good psychometric properties.⁷⁴ The DINE measures parent-child interactions by coding three subscales: parent behaviors, child behaviors, and child eating behaviors. DINE coding will be completed by research assistants trained by the PI. The research assistants will be blinded to the intervention condition. Each video will be double-coded, and discrepancies will be resolved by meetings between the two coders and consultation with the PI.
- Exit survey: Parents will complete an exit survey at the 3 month visit via RedCap on their feelings about the study and offer a chance to give feedback on their experiences.

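### Disputed DINE mealtime codes are settled with input from the PI, who very likely knows the parent's arm, and nothing masks the arm or the visit at that step

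*Combined protocol and SAP*

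**What the plan says.** Section 4.0 (Observational Behavioral Coding), repeated in section 11.0, covers the coding of the mealtime recordings made at baseline, post-intervention and 3 months:

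- Coders: "DINE coding will be completed by research assistants trained by the PI".
- Masking: "The research assistants will be blinded to the intervention condition".
- Disagreements: every video is coded twice, and "discrepancies will be resolved by meetings between the two coders and consultation with the PI".

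Section 10.0 describes what else the PI does. On training, "interventionists in both arms will be trained using didactics and role playing with the PI". On recording, "Intervention fidelity will be monitored by audio recording all sessions". The PI then "will review video recordings each week and conduct weekly supervision". The same section calls the trial single blind, meaning that participants do not know their arm.

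Section 2.1 makes positive parent behavior at an observed meal the secondary aim. Section 28.0 (10.4) assesses it with the RCI, success being a value above 1.96. The RCI is calculated for PACT participants only, from baseline to post-treatment and to follow-up.

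**The concern.** The DINE is the only outcome in section 4.0 that an observer scores from behavior; the other scales are completed by the parent. Much of its value therefore rests on masked coding. The plan masks the two coders, then brings in a third person for the codes on which they differ, and that person's other duties very likely reveal the arm. Discrepant codes are the ambiguous ones, where expectation has most room to act. PACT-F also teaches positive mealtime interaction (section 6.0), which is the behavior being coded.

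At stake is the credibility of the secondary-aim readout, a set of individual reliable-change results in 20 PACT parents with no control comparison specified beside it.

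**Working it through.** The plan states no figure to reproduce, so the check is mainly a comparison of passages.

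**1. Who is masked, and to what**

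| Person | Part in the DINE score | Masking stated |
|---|---|---|
| Parent | Is observed | Arm, until after the 3-month follow-up (10.0) |
| Two research assistants | Code each video | Arm (4.0, 11.0); nothing on visit |
| PI | Trains coders; is consulted on discrepancies | None |

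No section removes participant ID, arm or visit before the PI is consulted, or names a different adjudicator. Section 4.0 also has a research assistant facilitate the recordings. It does not say whether that person may code them, so coders may know the visit.

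**2. What the PI can learn.** PACT-F covers acceptance and commitment skills and mealtime interaction; control covers nutrition and *MyPlate* (section 6.0). Reviewing one session is enough to reveal the arm. The sentence on weekly review does not itself say that it covers both arms. The sentences around it point that way: both arms are manualized, the PI trains both sets of interventionists, all sessions are recorded, and no arm is exempted. (The text says audio for recording and video for review; I read both as session recordings.)

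**3. Which codes are exposed.** Agreed codes are not. Among disputed codes, the share shaped by the PI could be anywhere from 0% (the coders settle everything themselves) to 100%. The documents give no discrepancy rate. Section 28.0 (10.3) sets an 80% inter-rater goal for free-text responses, but nothing comparable is stated for the DINE.

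**4. How a shift would reach the RCI.** Let adjudication add b0 to a parent's baseline score and b1 to a later score. Then

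observed change = true change + measurement error + (b1 − b0).

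All parents in this analysis are in the PACT arm. If knowing the arm moved every visit equally, b1 = b0 and the bias would be zero. Inflation needs b1 > b0, so the visit must be known or guessed as well.

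**5. Sensitivity illustration (assumed inputs only).** Suppose b1 − b0 = d baseline SDs, reliability is r, errors are normal and true change is zero. The standard error of the difference is SD × √(2(1 − r)), so

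P(RCI > 1.96) = P(Z > 1.96 − d/√(2(1 − r))).

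| d (assumed) | r = 0.8 | r = 0.9 | Expected false responders among 20, one visit |
|---|---|---|---|
| 0 | 2.5% | 2.5% | 0.5 |
| 0.3 | 6.9% | 9.9% | 1.4 to 2.0 |
| 0.5 | 12.1% | 20.0% | 2.4 to 4.0 |

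Example: d = 0.3, r = 0.8 gives 1.96 − 0.3/0.632 = 1.486 and a tail of 6.9%; 20 × 0.069 = 1.4. The 20 is the active-arm target in section 8.0. The values of d and r have no source in the documents. The table shows how sensitive the RCI would be to a shift; it does not estimate one. Holding d fixed while r rises is also artificial: if higher reliability reflects better coder agreement, fewer codes would reach the PI and d should shrink.

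**The case against.** The strongest reply is that the plan breaks no promise. It claims masking for the research assistants and the participants, never for the PI or for adjudication. Both coders are masked to arm, the text puts their own meeting first, and consultation may be purely advisory. The outcome is secondary, in a 30-parent pilot that sets statistical significance aside. All of this stands, and it limits the point to disputed codes. It does not supply the missing safeguard.

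A reader might infer more than the documents support:

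- *That the final DINE score is unblinded.* Agreed codes remain masked to arm; only adjudicated ones are exposed.
- *That the PI certainly knows every parent's arm.* This is a strong inference from section 10.0, but it is not stated.
- *That the PI has a developer's stake in PACT-F.* Section 3.0 credits the adaptation to the team and does not identify the PI as developer.
- *That any effect could never be separated out.* Double coding yields two sets of codes made before consultation. If they are kept, the effect of adjudication can be examined. The plan does not say whether they are kept or discarded.
- *That a bias of a given size is to be expected.* The 0.3 and 0.5 SD shifts are assumptions, and zero is also possible.

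**Conclusion.** The point holds in a bounded form. Followed as written, the plan lets a person who very likely knows the arm influence disputed codes for the secondary outcome, and it masks neither arm nor visit at that step. The share of codes affected and the size and direction of any bias cannot be derived from the documents.

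The conclusion rests on two readings: that weekly review and supervision extend to both arms, and that the absence of any stated masking means none is planned. If the PI is in fact masked during consultation, stating the procedure would largely answer the point about the PI. Masking of visit for the coders would still need to be addressed, because the RCI is a within-arm change. This is worth correcting before coding starts, but it does not undermine the feasibility aims.

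**What to change.** In sections 4.0 and 11.0:

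1. The two blinded coders resolve discrepancies by consensus against the DINE manual.
2. PI input is limited to questions about code definitions, asked without the video, participant ID, arm or time point.
3. Videos go to coders in random order, with arm and visit labels removed where feasible.
4. Both original independent sets of codes are kept, and inter-rater agreement is reported on them rather than on the consensus codes.

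In section 28.0 (10.4), add a sensitivity analysis that repeats the DINE RCI on pre-consensus scores, for example the mean of the two coders' subscale scores. Averaging belongs at subscale level, because individual codes may be categorical and have no meaningful mean.

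The cost is small. A few hard codes are settled without the most experienced reviewer, randomizing the coding order means holding videos until a batch is available, and there is a little more analysis. No extra staff are needed.

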5.0 Study Design*

Study Design. This feasibility pilot study.

6.0 Study Intervention/Investigational Agent*

Active Treatment (PACT-F) and Control Interventions. Parents randomized to PACT-F will complete two 90-minute PACT-F sessions individually with a study interventionist, 2-weeks apart. Parents randomized to the control group will complete two 90-minute sessions individually with a study interventionist, 2-weeks apart (focused on nutrition education). The control intervention will be parallel

SHORT TITLE: PACT Study

to the PACT-F intervention, equal in the number of interactive components and duration of face-to-face time with health professionals (interventionists). Interventionists for both conditions will be individuals with at least master's-level training in mental health or a related field. Based on guidance from our parent consultants, we will deliver intervention sessions through Microsoft Teams to reduce barriers to participation (e.g., travel, childcare).

PACT-F. PACT-F is a 2-session intervention based on the Focused Acceptance and Commitment Therapy treatment literature^{14,30} and the two-session PACT approach utilized by Brown¹⁶ and Whittingham¹⁵ with parents of children with neurodevelopmental conditions. PACT-F content includes 1) education about parent MH problems among parents of children with PFD, 2) interactive learning of FACT skills, including cognitive defusion, mindfulness, and value-based decision making, and 3) education about the importance of positive parent-child interactions at mealtime and how to apply PACT-F skills to their mealtime interactions with their child with PFD. Each session lasts 90 minutes and will be conducted remotely via Microsoft Teams.

Control. The content of the control intervention covers a range of nutrition and healthy lifestyle topics including USDA's *MyPlate*. The control condition has equivalent face-to-face time with the interventionists.

